13.2 Safety and Tolerability Assessments

13.2.1 Body Weight

Body weight (kg) will be measured daily up to Day 3 and before and after each HD session as outlined in the Study Events Flow Chart ([Section 6](#)).

13.2.2 Physical Examination

A full physical examination will be performed as per Study Events Flow Chart ([Section 6](#)) and will include, at a minimum, assessment of the following systems: skin, head, ears, eyes, nose and throat, respiratory system, cardiovascular system, gastrointestinal system, neurological condition, blood and lymphatic systems, and the musculoskeletal system.

Abbreviated physical examinations will include at the minimum, examination of respiratory, cardiovascular, and gastrointestinal systems, with the option for further examination of additional systems as necessary based on reported symptoms/AEs.

Symptom-driven physical examination may be performed at other times if deemed necessary by the PI or designee.

13.2.3 Vital Signs

Single measurements of body temperature, respiratory rate, blood pressure, and heart rate, will be measured as outlined in the Study Events Flow Chart ([Section 6](#)). Additional vital signs may be taken at any other times if deemed necessary.

Vital signs will be performed with patients in a seated position following a 5 minute rest period, except when they are supine or semi-reclined because of study procedures and/or AEs (e.g. nausea, dizziness) or if deemed necessary by the PI or designee.

When scheduled prior to HD, vital signs will be performed within 1 hour prior to the start of the HD. When scheduled post-dose, vital signs will be performed within approximately 15 minutes of the scheduled time point.

13.2.4 ECG Monitoring

Single 12-lead ECGs will be performed as outlined in the Study Events Flow Chart ([Section 6](#)). Additional ECGs may be taken at any other times if deemed necessary by the PI or designee.

ECGs will be performed with patients in a semi-recumbent position following a 5 minute rest period. All ECG tracings will be reviewed by the PI or designee.

When scheduled post-dose, ECGs will be performed within approximately 20 minutes of the scheduled time point.

13.2.5 Vascular Access Site Reaction Assessment

The monitoring of AEs will include assessment of HD vascular access fistula (or AV graft) site reactions. The preferred vascular access is an established AV fistula (or AV graft). Well established and reaction-free AV graft is an alternative, but less preferred access option, as it is more prone to complications. Patients who are hemodialyzed through catheters are not included in the study. Therefore, inspection of the AV fistula (or AV graft) and surrounding area will be performed. Any new abnormal findings inconsistent with past skin injuries as expected in patients on chronic HD will be reported as AEs. AV fistula (or AV graft) site reactions will be evaluated as outlined in the Study Events Flow Chart ([Section 6](#)). Prior to HD, the AV fistula (or AV graft) site will be examined for inflammation, infection, or flow abnormalities (including occlusion of the fistula or graft). When scheduled post-dose, injection site examinations will be performed within approximately 20 minutes after completion of the HD session. Reactions will be rated according to the FDA Guidance for Industry: Toxicity Grading Scale for Healthy Adult and Adolescent Volunteers Enrolled in Preventive Vaccine Clinical Trials [[11](#)] as follows:

Local Reaction	Mild (Grade 1)	Moderate (Grade 2)	Severe (Grade 3)
Pain	Does not interfere with activity	Repeated use of non-narcotic pain reliever > 24 hours or interferes with activity	Any use of narcotic pain reliever or prevents daily activity
Tenderness	Mild discomfort to touch	Discomfort with movement	Significant discomfort at rest
Erythema/Redness*	2.5 – 5 cm	5.1 – 10 cm	> 10 cm
Induration/Swelling**	2.5 – 5 cm and does not interfere with activity	5.1 – 10 cm or interferes with activity	> 10 cm or prevents daily activity

* In addition to grading the measured local reaction at the greatest single diameter, the measurement should be recorded as a continuous variable.

** Induration/swelling should be evaluated and graded using the functional scale as well as the actual measurement.

13.2.6 Bleeding of Access Site

Evaluation of bleeding and bleeding time from the HD vascular access sites on the AV fistula or AV graft using the ladder or buttonhole technique will be performed as per Study Events Flow Chart ([Section 6](#)).

Following HD, the needle will be removed from the vascular access site and immediately followed by the placement of the dressing (i.e., gauze). Pressure will be applied manually by a clinical associate for 10 minutes before checking for evidence of bleeding around the dressing. If there is still some bleeding, pressure will be applied back at the site for 5 minutes. The site will then be checked again for evidence of bleeding; this procedure will be repeated every 5 minutes until bleeding has stopped. Once bleeding has stopped, a new gauze dressing is applied and then taped. To ensure consistency when applying the pressure, the clinical staff will have received adequate training and an attempt will be made to have the same associates perform this test.

The time to clot will be recorded.

13.2.7 Clinical Laboratory Tests

All tests listed below will be performed as per Study Events Flow Chart ([Section 6](#)). In addition, laboratory safety tests may be performed at various unscheduled time points, if deemed necessary by the PI or designee.

Hematology

- Hemoglobin
- Hematocrit
- Total and differential leukocyte count
- Red blood cell count
- Platelet count

Coagulation

- PT/INR
- aPTT
- Fibrinogen
- Thrombin time (TT)

Urinalysis⁺

- pH
- Specific gravity
- Protein***
- Glucose
- Ketones
- Bilirubin
- Blood***
- Nitrite***
- Urobilinogen
- Leukocyte esterase***

Serum Chemistry*

- BUN
- Bilirubin (total and direct)
- Alkaline phosphatase
- AST
- ALT
- Lactate dehydrogenase
- Albumin
- Sodium
- Potassium
- Bicarbonate
- Chloride
- Glucose
- Creatinine**

Additional Tests

- HIV test
- HBsAg
- HCV
- Saliva drug screen
 - Opiates
 - Amphetamines
 - Cocaine
 - Cannabinoids
- Saliva or breath alcohol screen
- Serum pregnancy test (for females only)
- FSH (for postmenopausal females only)

* Samples for serum chemistry will be obtained following a fast of at least 4 hours, however, in case of dropouts or rechecks, patients may not have fasted for 4 hours prior to the serum chemistry sample is taken.

** At screening, creatinine clearance will be calculated using the Cockcroft-Gault formula.

*** If urinalysis is positive for protein, blood, nitrite and/or leukocyte esterase, a microscopic examination (for red blood cells, white blood cells, bacteria, casts, and epithelial cells) will be performed.

+ May not be performed for anuric patients.

13.2.8 Adverse Events

13.2.8.1 Adverse Event Definition

AE will be defined as any untoward medical occurrence during the study, associated or not with the use of E-WE thrombin in the study patients, whether or not considered drug-related. TEAE is an AE that occurs after administration of the study drug or matching placebo.

A suspected adverse reaction means any AE for which there is a reasonable possibility that the drug caused the AE. Reasonable possibility means there is evidence to suggest a causal relationship between the drug and the AE.

An AE can, therefore, be any unfavorable and unintended sign (including an abnormal laboratory finding), symptom, or disease that is temporally associated with the use of a medicinal (investigational) product, whether or not related to the medicinal (investigational) product [12].

13.2.8.2 Monitoring

Patients will be monitored for AEs from check-in through completion of the study. Patients will be asked how they are feeling once per day during confinement and at each return/follow-up visit.

AEs (whether serious or non-serious) and clinically significant abnormal laboratory test value(s) will be evaluated by the PI or designee and treated and/or followed up until the symptoms or value(s) return to normal, or acceptable levels, as judged by the PI or designee.

Treatment of SAEs will be performed by a licensed medical provider, either at the CRU or at a nearby hospital emergency room. Where appropriate, medical test(s) and/or examination(s) will be performed to document resolution of event(s). The outcome may be classified as resolved, improved, unchanged, worse, fatal, or unknown (lost to follow up).

13.2.8.3 Reporting

All AEs that occurred during this clinical study (i.e., before, during, and after exposure of ESRD patients to E-WE thrombin) will be recorded. This design is to improve Sponsor ability to obtain reliable initial information about drug safety yet reducing the number of study patients needed to generate useful information.

AEs and SAEs, including those related to study participation (e.g., protocol-mandated intervention), will be recorded from the time of patient check-in until study completion.

AEs will be coded using the most current Medical Dictionary for Regulatory Activities (MedDRA)[®] available at Celerion.

The PI or designee will review each event and assess its relationship to study drug (likely, probably, possibly, unlikely, or unrelated) and severity. The date and time of onset, time relationship to drug dosing, duration, and outcome of each event will be noted.

Relationship of AE:

The relationship of each AE to the study drug will be assessed using the following definitions:

Unrelated	
 ▪ The adverse event must clearly be caused by the participant's clinical state, or the study procedure/conditions ▪ Definitely not related to drug ▪ Temporal sequence of an adverse event onset relative to administration of drug not reasonable ▪ Another obvious cause of an adverse event
Unlikely	
 ▪ Time sequence is unreasonable ▪ There is another more likely cause for an adverse event
Possibly	
 ▪ Corresponds to what is known about the drug ▪ Time sequence is reasonable ▪ Could have been due to another equally, likely cause
Probably	
 ▪ Is a known effect of the drug ▪ Time sequence from taking drug is reasonable ▪ Ceases on stopping the drug ▪ Cannot be reasonably explained by the known characteristics of the participant's clinical state
Likely	
 ▪ Is a known effect of the drug (e.g. listed in IB) ▪ Time sequence from administering drug is reasonable ▪ Event stops upon stopping drug and returns upon restarting drug

Severity of AE:

Severity rating used during the study will be based on the toxicity grading scale tables present in the FDA (Center for Biologics Evaluation and Research) toxicity grading scale for healthy volunteers 4-point severity scale (Grade 1, 2, 3 and 4) [11].

The following definitions for rating severity will be used for AEs not identified in the guidance:

Mild (Grade 1)	The AE does not interfere with daily activity.
Moderate (Grade 2)	The AE interferes with daily activity, but no medical intervention is required.
Severe (Grade 3)	The AE prevents daily activity and requires medical intervention.
Potentially Life-threatening (Grade 4)	Emergency room visit or hospitalization is required.

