A placebo arm is included in this study design in order to robustly demonstrate the safety and efficacy of E-WE thrombin while not placing the patients at unnecessary risk, as mentioned above. The primary endpoint in this study is safety, measured as the number or frequency/rate of AEs that occur during the comparable observation periods. A heparin-free inpatient HD observation period (from Day -8 to Day 1 prior to dosing) is included in the trial design to establish a baseline for the heparin-free procedure. Continuation of the heparin-free HD procedure during the subsequent trial period and inclusion of a placebo arm allows for the determination of whether an AE is drug-related or not and permits accurate assessment of the safety of the study drug. The addition of a placebo arm also removes potential bias from the interpretation of AEs by the PIs and from the reporting by the patients. The secondary endpoint for this study is efficacy of E-WE thrombin on HD which may be more clearly observed with a placebo control instead of an active control (e.g., heparin). While the placebo arm may be at the same risk of clotting within the dialysis circuit as during the pre-dosing period (Days -8 to 1), data cited above suggests that these patients will not be at higher risk for either thromboembolic or bleeding complications. Should clotting occur within the dialyzer cartridge during a HD session that results in dialyzer failure, the dialyzer cartridge will be replaced, and the patient will be closely monitored by

the PI. It is important to note that replacement of the dialyzer cartridge during HD is safe for the patient and a routine procedure in cases of dialyzer failure.

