10.1.2 Study Duration

The total planned duration of patient participation is approximately 50 days from screening to follow-up.

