11.4 Study Restrictions

11.4.1 Prohibitions and Concomitant Medication

Consumption of foods and beverages containing the following substances will be prohibited as indicated:

- Xanthines/caffeine: 48 hours prior to dosing and throughout the period of sample collection (small amounts of caffeine derived from normal foodstuffs e.g., 250 mL/8 oz./1 cup decaffeinated coffee or other decaffeinated beverage, per day, with the exception of espresso; 45 g/1.5 oz. chocolate bar, per day, would not be considered a deviation to this restriction);
- Alcohol: 48 hours prior to dosing and throughout the period of sample collection;

Concomitant medications will be listed, recorded, and allowed except for those listed as prohibited in the exclusion criteria in [Section 11.2](#). It is understood and will be considered that treatment with certain drugs or cessation of treatment with certain drugs may have adverse effects and could interfere with the evaluation of the primary outcome measures of the study. Apart from anticoagulant/antiplatelet agents, no patient will be requested to stop taking any medication to be able to participate in the trial.

Acetaminophen (up to 2 g per 24 hours) or opioids may be administered, for fever or chronic pain control, at the discretion of the PI or designee. Administration of opioids for certain types of pain management may be allowed.

If deviations occur, the PI or designee in consultation with the Sponsor if needed will decide on a case-by-case basis whether the patient may continue participation in the study.

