15.1.3 Subject Information and Consent

The purpose of the study, the procedures to be carried out and the potential hazards will be described to the subjects in non-technical terms. Subjects will be required to read, sign and date an ICF summarizing the discussion at screening, and will be assured that they may withdraw from the study at any time without jeopardizing their medical care.

Subjects will be given a copy of their signed ICF.

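### AE and SAE recording starts at check-in, so a serious event in screening, including one after a study-requested stop of an antithrombotic drug other than dialysis heparin, has no clear capture rule

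*Protocol*

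**What the plan says.** Two protocol sections fix the start at check-in, which section 10.1.1 places on Day -8. Section 13.2.8.2 says: "Patients will be monitored for AEs from check-in through completion of the study". Section 13.2.8.3 uses the same start for recording, and expressly includes events caused by taking part: "AEs and SAEs, including those related to study participation (e.g., protocol-mandated intervention), will be recorded from the time of patient check-in until study completion".

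Consent comes earlier. Section 15.1.3 says: "Subjects will be required to read, sign and date an ICF summarizing the discussion at screening".

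Other text is broader and gives no start day. Section 13.2.8.3 opens with: "All AEs that occurred during this clinical study (i.e., before, during, and after exposure of ESRD patients to E-WE thrombin) will be recorded". Section 13.2.8.1 says: "AE will be defined as any untoward medical occurrence during the study". Section 10.1 treats the screening period as part of the study, and section 10.1.2 says: "The total planned duration of patient participation is approximately 50 days from screening to follow-up". Section 13.2.8.4 requires every SAE to reach the sponsor within one working day of the site learning of it, without saying when that duty begins.

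On medication, exclusion 2 in section 11.2 bars anticoagulant and antiplatelet agents, including NSAIDs, for the 2 weeks before check-in. Unfractionated heparin during dialysis is exempt until check-in. Section 11.4.1 adds: "Apart from anticoagulant/antiplatelet agents, no patient will be requested to stop taking any medication to be able to participate in the trial". The same section accepts that stopping certain drugs may itself cause harm.

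**The concern.** By implication, section 11.4.1 makes antithrombotic drugs the one class a patient may be asked to give up in order to take part. A patient who stops such a drug during screening, to meet exclusion 2, is exposed to a consequence of the study before AE recording starts. Section 8.4 describes these patients as prone to thromboembolism and acute ischemic cardiovascular events even when stable on dialysis.

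What is at stake is participant protection. If a serious event follows such a stop, staff working from section 13.2.8.3 need not record it, and could reasonably conclude that the one-working-day duty has not begun. The gap is widest for a patient who is then never dosed.

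**Working it through.** This needs only study-day arithmetic and a reading of the sections side by side. The plan states no figure for the unrecorded interval.

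1. **Latest stop that satisfies exclusion 2.** Check-in on Day -8, minus 14 days, is Day -22.
2. **Shortest unrecorded interval after such a stop.** Day -22 to Day -8 is 22 − 8 = 14 days.
3. **Longest interval for a stop made after consent.** By flow chart footnote b, screening falls within 28 days before Day -8, so it starts on Day -36: 36 − 8 = 28 days. By the flow chart's screening column it starts on Day -37: 37 − 8 = 29 days.
4. **Whether the protocol counts screening as participation.** Day -36 to Day -8 is 28 days. Day -8 to Day 1 is 8 days, as section 10.1 states (there is no Day 0). Day 1 to Day 14 is 13 days. The sum is 28 + 8 + 13 = 49, or 29 + 8 + 13 = 50 from Day -37. This reproduces the approximately 50 days of section 10.1.2, so the time before check-in is counted as participation.
5. **Dialysis heparin.** It is allowed until check-in and withheld during confinement, so its unrecorded interval is about 0 days.
6. **Whether the opening of section 13.2.8.3 closes the gap.** It promises recording before exposure, but section 8.3.1 supplies a recorded pre-exposure period: "A heparin-free inpatient HD observation period (from Day -8 to Day 1 prior to dosing) is included in the trial design". That period satisfies the opening sentence without reaching into screening, and the later, specific sentence names check-in.
7. **Whether section 13.2.8.4 closes it.** Together with sections 13.2.8.1 and 10.1, it can be read to cover SAEs in screening. Section 13.2.8.3 points the other way for recording. On the combined reading, an SAE is reportable before it has to be recorded.
8. **Whether other capture closes it.** The flow chart repeats the eligibility check at check-in. Exclusion 1 (thrombotic event or access failure in the past 3 months), exclusion 7 (clinically significant acute illness within 2 weeks of check-in) and exclusion 9 (including active bleeding) would remove most patients with such an event. None of these requires an AE or SAE entry. SAP Appendices 16.2.4.3 (medical history), 16.2.5.2 (eligibility at check-in) and 16.2.5.11 (medications) are limited to the Safety Population, which contains dosed patients only. The Day 14 visit is also for dosed patients only.

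I have not relied on the flow chart's AE monitoring row, because its start column is not legible in the text version of the protocol.

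**The case against.** The strongest opposing case has four parts.

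**The stop is inferred.** Exclusion 2 is an eligibility bar and instructs nobody to stop a drug. The inference rests on one clause of section 11.4.1, part of which dialysis heparin explains. This stands as a limit on size: no document says that any patient will be taken off another drug. It does not remove the point, because the clause also names antiplatelet agents, which heparin does not explain.

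**The eligibility recheck already protects patients.** It does keep a patient with a recent event from being dosed, and exclusion 7 covers almost exactly the 14 days in question. But screening a patient out is not the same as recording and reporting what happened.

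**SAEs in screening are already reportable.** Sections 10.1, 13.2.8.1 and 13.2.8.4 give this real support. A reader might infer that the protocol waives SAE reporting before check-in, and the text does not go that far. What remains is a conflict with section 13.2.8.3, on a duty that staff must meet within one working day.

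**Nothing in the analysis changes.** This is correct. A reader might infer that the safety comparison is biased. It is not, because the TEAE tables start at dosing and the pre-treatment comparison uses Day -8 to Day 1, which is recorded.

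**Conclusion.** The point holds as a gap in participant protection and a conflict of wording. It does not threaten the trial's results. For a patient asked to stop a barred drug other than dialysis heparin, the unrecorded interval is at least 14 days, and at most 28 (or 29 by the flow chart) if the stop follows consent. These are calendar spans, not measures of risk. The number of patients is unknown and may be zero. The barred list includes NSAIDs, so not every stop carries thrombotic risk.

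Two stronger readings should be set aside. One is that every study-driven anticoagulant stop falls in the gap: heparin withdrawal, the one stop the protocol expressly requires, falls inside the recorded period. The other is that patients are taken off drugs before they consent: no section shows this, and section 15.1.3 places consent at screening.

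The conclusion assumes that section 11.4.1 means what it implies, and that the specific check-in sentence of section 13.2.8.3 governs recording. The change is worth making because it is cheap.

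**What to change.** In sections 13.2.8.2 and 13.2.8.3, require that all SAEs, and AEs related to protocol-required procedures or study-requested medication withdrawal, be recorded from signature of the consent form, whether or not the patient is later dosed. Keep check-in as the start for all other AEs. In section 13.2.8.4, state that the one-working-day duty begins at consent too. For these events, the unrecorded interval after consent then falls from at least 14 days to 0.

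The cost is a small wording amendment with IRB approval and slightly more site reporting during screening. No visits or patients are added, and the TEAE tables do not change. A separate SAP listing of these events is optional. A further rule that consent must precede any drug stop is not needed on the present text.

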10. INVESTIGATIONAL PLAN

10.1 Overall Study Design and Plan

This is a phase 2, randomized, double-blind, placebo-controlled, single-dose study of E-WE thrombin designed to evaluate the safety and efficacy at 2 dose levels administered to patients with ESRD during HD conducted at one study center in the US.

Patients will be enrolled in Cohort 1 or Cohort 2; cohorts will be dosed sequentially. Dosing of Cohort 2 will commence following completion of all study events for all patients in Cohort 1. Within each cohort, patients will be randomized to receive active drug or matching placebo as summarized below:

Table 1. Cohort and Treatment Randomization

Cohort	Treatment	Active:Placebo	Cohort Size
1	0.5 µg/kg bolus dose administered into the dialysis line immediately followed by a 0.25 µg/kg/hour continuous infusion dose into the dialysis line over 4 hours of E-WE thrombin or matching placebo, for a total dose of 1.5 µg/kg	2:1	12:6
2	1 µg/kg bolus dose administered into the dialysis line immediately followed by a 0.5 µg/kg/hour continuous infusion dose into the dialysis line over 4 hours of E-WE thrombin or matching placebo, for a total dose of 3 µg/kg	2:1	12:6

This study includes a screening period of 28 days prior to checking in to the CRU on Day -8. From Day -8 (8 days prior to dosing on Day 1) through Day 3, all patients will undergo HD 5 times and will be assessed for all scheduled procedures and endpoints before and after each HD session as per the Study Events Flow Chart ([Section 6](#)), using only one type of dialyzer cartridge for each patient.

On Day 1, prior to dosing, patients will undergo baseline measurements followed by initiation of a regular HD procedure, consistently using only one type of dialyzer cartridge for each patient. A single dose of E-WE thrombin or matching placebo will be administered into the dialysis line during the HD procedure. Patients will continue to undergo HD procedures and scheduled assessments from Day 1 through Day 3.

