13.2.8.4 Serious Adverse Events

If any AEs are serious, as defined by the FDA Code of Federal Regulations (CFR), Chapter 21, special procedures will be followed. All SAEs will be reported to the Sponsor via fax or e-mail within one working day of becoming aware of the event, whether or not the serious events are deemed drug-related. All serious event reporting will adhere to 21 CFR 312.32 for Investigational New Drugs (IND) and to the Guidance for Industry and Investigators: Safety Reporting Requirements for INDs and BA/BE, dated December 2012 [12]. The institutional review board (IRB) will be notified of the Alert Reports as per FDA regulations.

An SAE is any AE or suspected adverse reaction that in the view of either the PI (or designee) or Sponsor, results in any of the following outcomes: Death, a life-threatening adverse event, inpatient hospitalization or prolongation of existing hospitalization, a persistent or significant incapacity or substantial disruption of the ability to conduct normal life functions, or a congenital anomaly/birth defect. Important medical events that may not result in death, be life-threatening, or require hospitalization may be considered serious when, based upon appropriate medical judgment, they may jeopardize the patient or subject and may require medical or surgical intervention to prevent one of the outcomes listed in the above definition. Examples of such medical events include allergic bronchospasm requiring intensive treatment in an emergency room or at home, blood dyscrasias or convulsions that do not result in inpatient hospitalization, or the development of drug dependency or drug abuse.

Life-threatening is defined as an AE or suspected adverse reaction that in the view of the PI (or designee) or Sponsor, its occurrence places the patient or subject at immediate risk of death. It does not include an AE or suspected adverse reaction that, had it occurred in a more severe form, might have caused death.

Unexpected is defined as an AE or suspected adverse reaction that is not listed in the IB or is not listed at the specificity or severity that has been observed; or is not consistent with the risk information described in the general investigational plan or elsewhere in the current application, as amended.

If a SAE occurs to a patient on this study, contact the Sponsor personnel listed in [Section 3](#).

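### The adverse-event relationship scale asks for re-challenge and prior knowledge of the effect, which does not suit a single-dose early-phase trial and makes causality ratings unreliable

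*Protocol*

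**What the plan says.** Protocol 10.1 describes a "randomized, double-blind, placebo-controlled, single-dose study". Section 12.1 gives each patient one bolus followed by a 4-hour infusion on Day 1.

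In 13.2.8.3 the investigator must "assess its relationship to study drug (likely, probably, possibly, unlikely, or unrelated) and severity", using a table of definitions. The criteria that matter here are:

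- **Likely**: a known effect (listing in the Investigator's Brochure is given as an example), reasonable timing, and "Event stops upon stopping drug and returns upon restarting drug".
- **Probably**: "Is a known effect of the drug", reasonable timing, cessation when the drug is stopped, and no reasonable explanation in the patient's clinical state.
- **Possibly**: "Corresponds to what is known about the drug", reasonable timing, and another equally likely cause.
- **Unlikely** and **Unrelated**: unreasonable timing and a more likely or obvious other cause.

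No sentence says whether a level needs all of its criteria or only one.

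Two nearby definitions do not depend on prior knowledge. Section 13.2.8.1: "A suspected adverse reaction means any AE for which there is a reasonable possibility that the drug caused the AE". Section 13.2.8.4: "Unexpected is defined as an AE or suspected adverse reaction that is not listed in the IB".

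SAP 7.3 tabulates treatment-emergent events by severity and relationship, in Table 14.3.1.3.

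**The concern.** A relationship scale should be usable with the data that the design produces, and should have a place for an effect that nobody has seen before. This one looks deficient on both counts. Recurrence on restarting is a criterion for repeated dosing. Prior knowledge of the effect presupposes a drug with an established safety profile.

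Here the knowledge base is small. The completed first-in-human study gave active drug to 16 healthy subjects, as a bolus only (Protocol 8.2.2 and 8.2.2.1). Section 8.4 states that hemostatic safety in end-stage renal disease on dialysis has not been established. Safety is the primary objective, so classifying new effects is part of what the trial is for. If the scale has no clear place for them, two careful investigators could rate the same event differently and both follow the text.

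**Working it through.** The plan states no figure on this point. The check is definitional, with a short calculation for context.

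**Step 1: set out the criteria (Protocol 13.2.8.3).**

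| Level | Prior knowledge | Timing | Other cause | De-challenge or re-challenge |
|---|---|---|---|---|
| Likely | known effect | reasonable | not mentioned | stops on stopping and recurs on restarting |
| Probably | known effect | reasonable | not explained by clinical state | stops on stopping |
| Possibly | fits what is known | reasonable | equally likely | not mentioned |
| Unlikely | not mentioned | unreasonable | more likely | not mentioned |
| Unrelated | not mentioned | unreasonable | clear or obvious | not mentioned |

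**Step 2: apply them to test events, under each way of combining criteria.** All events have reasonable timing and no re-challenge.

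| Event | All criteria required | Any one sufficient |
|---|---|---|
| A. Not known, does not fit what is known, no other cause | none of 5 | Possibly, Probably, Likely |
| B. Not known, fits the known pharmacology, no other cause | none of 5 | Possibly, Probably, Likely |
| C. Not known, fits the known pharmacology, equally likely other cause | Possibly | Possibly, Probably, Likely |
| D. Not known, does not fit what is known, more likely other cause | none of 5 | Unlikely, Possibly, Probably, Likely |
| E. Known effect, no other cause, stops on stopping | Probably | Possibly, Probably, Likely |

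For A to D the result is the same with or without de-challenge. In the right-hand column, reasonable timing alone is enough for the three upper levels, because it is listed in each of them. Event E shows the re-challenge problem separately: with all criteria required, even a well-recognised effect stops at Probably.

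**Step 3: can re-challenge occur?** One dose is planned. Section 12.2 bars any modification of dose or administration and discontinues the patient instead. Section 12.1 provides for documenting infusion-rate changes made because of an adverse event. The two sections contradict each other and must be reconciled. Neither plans a stop followed by a restart.

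**Step 4: compare the scale with the protocol's own definitions.** Section 13.2.8.1 asks for a reasonable possibility, explained as evidence pointing to causation. Section 13.2.8.4 recognises suspected reactions that the Investigator's Brochure does not list. Read with all criteria required, 13.2.8.3 cannot rate a reaction that is not a known effect above Possibly, and it reaches Possibly only in case C. No text says which of the five levels amount to a reasonable possibility.

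**Step 5: check the SAP shell.** The Table 14.3.1.3 shell has relationship columns for Unrelated, Unlikely, Possibly and Probably. Each row has 10 value cells: 2 counts + 4 severity grades + 4 relationship levels = 10. The missing fifth level therefore does not look like a loss in text extraction.

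**Step 6: how plausible is a new effect?** For a reaction seen in 0 of 16 subjects, the one-sided 95% exact upper bound on its rate is 1 − 0.05^(1/16) = 17.1%. The rates p below are assumptions, not figures from the documents. The active group here is 2 × 12 = 24.

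| Assumed rate p | No case in 16: (1 − p)^16 | At least one in 24: 1 − (1 − p)^24 |
|---|---|---|
| 5% | 44% | 71% |
| 10% | 19% | 92% |
| 15% | 7% | 98% |

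An effect absent from the earlier study could readily appear in this one.

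**The case against.** The strongest reply is that an experienced investigator reads such tables as guidance and takes the nearest level. Event A meets one criterion of Possibly and none of Unlikely, so Possibly is the natural choice. In the first-in-human study a headache about 10 minutes after dosing was rated possibly related (8.2.2.1), although the scale used there is not given. Many real events would also resemble case C: 8.4 notes that any drug can provoke allergic reactions and that these patients are prone to many adverse events, so a competing cause will often exist. This stands as a limit on how often the gap matters. It does not remove the gap, because the rating then rests on judgement that the protocol does not record.

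Three stronger readings are tempting, and the documents do not support them.

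- *New reactions are biased toward Unlikely.* Event A meets no Unlikely criterion, and if any one criterion suffices it qualifies for the upper levels. With the combination rule unstated, no direction can be claimed.
- *Expedited reporting is compromised.* Section 13.2.8.4 sends every serious event to the sponsor whether or not it is thought drug-related, and nothing makes the five-level scale decide expedited reporting.
- *The problem can be sized by how little of follow-up falls within the infusion.* Clock time does not measure risk. The drug is thought to clear within seconds to minutes (8.1), and the biomarker effects had returned to baseline by 24 hours (8.2.2.2).

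The effect on the primary objective is also bounded. The primary measures include the number and severity of events against pre-treatment and placebo (9.2), and 8.3.1 relies on the placebo arm to judge drug-relatedness. Tables 14.3.1.1 and 14.3.1.2 do not use the scale. SAP section 10 also warns that the shells may not reflect every aspect of the study.

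**Conclusion.** The point holds as a defect in the definitions. The re-challenge criterion does not match a single-dose design, and all three upper levels list prior knowledge that the protocol's own definition of a suspected reaction does not ask for. A previously unknown event with reasonable timing and no other cause fits 0 of 5 levels if all criteria are required, and 3 of 5 at once if any suffices. Both readings fail, so the conclusion does not depend on choosing between them. The 0-of-5 result itself does assume that all criteria are required, and it does not extend to case C.

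A reader might also infer that no patient could ever be rated Likely. That is too absolute: the unresolved conflict between 12.1 and 12.2 leaves a stop and restart within the infusion theoretically open, although none is planned.

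The consequence is unreliable causality classification in Table 14.3.1.3 and in the relationship column of the adverse-event listing, together with an SAP shell that is one level short. Counts and severity of events are untouched.

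**What to change.** In Protocol 13.2.8.3:

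1. Remove recurrence on restarting as a requirement for Likely.
2. Make known effect and cessation on stopping supportive, to be considered where applicable, rather than required.
3. Let Possibly include events not previously known, when timing is reasonable and there is evidence pointing to a causal link. Merely being unable to exclude the drug would be looser than 13.2.8.1.
4. State how the criteria within a level combine.
5. State which levels count as the reasonable possibility of 13.2.8.1.

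In the SAP, give Table 14.3.1.3 all five protocol levels. Separately, reconcile 12.1 and 12.2 on infusion changes.

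The cost is wording in the protocol, the CRF completion guide and one SAP shell, through an amendment approved under 15.8 by the sponsor, the investigator and the IRB, plus brief site retraining. Somewhat more events may be rated as related. No treatment or assessment changes.
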